4.4.2.2. Others laboratory parameters

For urinary biochemistry and cryoglobulins parameters, descriptive statistics on value at baseline, at each post-baseline visit under treatment and last post-baseline value under treatment will be performed.

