8.1. Specification of safety parameters

Safety measurements performed during the study are indicated in [Table \(4.1.2\) 1](#).

- **Adverse events,**
- **Physical examination,**
- **Body weight (kg),**
- **Vital signs:**
 - Systolic blood pressure (SBP) (mmHg)
 - Diastolic blood pressure (DBP) (mmHg)
 - Pulse Rate (bpm)
 - Body temperature
- **12-lead ECG,**
- **Laboratory examinations (serum biochemistry and haematology, pregnancy tests, coagulation tests, cryoglobulins, urinalysis):**
 - **Serum biochemistry (central):** Albumin, total protein, C reactive protein (CRP), alkaline phosphatase, total bilirubin, gamma glutamyltransferase (GGT), aspartate amino transferase (AST), alanine amino transferase (ALT), lipase, amylase, bicarbonate, calcium, chloride, potassium, sodium, lactate dehydrogenase (LDH), creatine kinase (CK), cholesterol, triglycerides, glucose, creatinine, urea and uric acid. If the total bilirubin concentration is increased above 1.5 times the upper limit of normal, direct and indirect reacting bilirubin should be differentiated.

In addition, **HbA1c** assay will be performed **locally** at screening for eligibility criteria and **ESR** will be also performed locally at each visit for the assessment of the inflammatory status.

- **Serum Haematology (central):** Hemoglobin, hematocrit, red blood cell count, white blood cell count with differential (*e.g.* neutrophils, basophils, eosinophils, monocytes, lymphocytes) and platelet count.
- **CD19 B cell count** performed **locally** at screening to check eligibility criterion n°30 (rituximab or other B cell depleting agent).
- **Urinalysis (local):** A semi-quantitative “dipstick” evaluation for the following parameters will be performed: specific gravity, pH, glucose, protein, bilirubin, ketones, nitrite, leukocytes and blood. If dipstick urinalysis is abnormal, microscopic examination for WBC, RBC, crystals, and casts will be performed.
- **Coagulation test (central):** Prothrombin time (PT), activated partial thromboplastin time (aPTT) will be measured.
- **Cryoglobulins (local):** at each ESSDAI assessment (ASSE, W000, W004, W013), cryoglobulins measurement will be performed (see [Section 7.2](#)). Cryoglobulin result obtained from a previous sampling performed within 1 month before screening visit could be used for ESSDAI scoring at screening.

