10.1.2.5.2. Clinical laboratory evaluation

For each laboratory parameter, the following analyses will be performed:

- Descriptive statistics on value at baseline, on value at each post-baseline visit under treatment, on last post-baseline value under treatment and on change from baseline to last post-baseline value under treatment,
- Number and percentage of patients with at least one high/low emergent abnormal value under treatment, according to the laboratory reference ranges and to the cut-offs for PCSA values.
- Laboratory parameters classified (number and percentage of patients in each class) according to these reference ranges and cut-offs, and using shift tables from baseline to the worst (high and/or low) values under treatment.

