1.1.2. Endpoints

The primary efficacy endpoint is the change from baseline in ESSDAI total score to W013.

The secondary efficacy endpoints are:

- ESSDAI score by domain and total score at each visit (value & change).
- ESSPRI score by symptom and total score at each visit (value & change).
- Proportion of patients with ≥ 3 points, ≥ 5 points, ≥ 7 points of improvement from baseline in ESSDAI at each visit.
- Proportion of patients with ≥ 1 point, ≥ 2 points, ≥ 3 points of improvement from baseline in ESSPRI at each visit.
- Proportion of patients with ≥ 3 points of improvement in ESSDAI and with ≥ 1 point of improvement in ESSPRI from baseline at each visit.
- Proportion of patients with a STAR total score ≥ 5 at each visit (value).
- Proportion of patients with a CRESS total score ≥ 3 at each visit (value).
- Fatigue (MFI) by domain, quality of life (SF-36) for mental and physical domains, physician and patient's global assessment of the disease activity (NRS) at each visit (value and change).
- Tear gland function: Schirmer's test and in OSS on the most affected eye and for the mean of both eyes at each visit (value and change).
- Salivary gland function: unstimulated and stimulated salivary flow rate at each visit (value and change).

The other secondary endpoints are:

- **Safety:** The safety and tolerability assessed by incidence of adverse events (AEs), change over time in safety parameters (vital signs, biological laboratory) and incidence of abnormal safety parameters throughout the study.
- **Pharmacokinetics:** Pharmacokinetics of S95011 in serum samples:
 - Pre-dose (before the start of the IMP infusion) at W000, W002, W004, W007, and W010.
 - Right after the end of the IMP infusion and in the [1-3h] interval after the end of the IMP infusion at W000 and W010.
 - Between W011 and W012, and at W013, W016, W019 and W028.

CL2-95011-001 - Statistical Analysis Plan | VV-TMF-116033 | 2.0

- **Pharmacodynamics:** Receptor Occupancy (RO) of S95011 in blood samples:
 - Pre-dose (before the start of the infusion) at W000, W002, W004, W007 and W010.
 - Right after the end of the infusion of the IMP at W000 and W010.
 - At W013, W019, W028.
- **Incidence of ADA** in serum samples:
 - Pre-dose (before the start of the infusion) at W000, W002, W004, W007 and W010.
 - At W013, W019, W028.

The exploratory endpoints are:

- **In blood:**
 - Lymphocytes subsets (PBMC) assessed at W000, W004, W007, W013.

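### The SAP leaves out, without declaring it, the protocol's emergent-abnormal counts and shift tables for urinalysis and cryoglobulins, so its planned tables show prevalence but not how many patients became newly abnormal

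*SAP*

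**What the plan says.** Protocol 10.1.2.5.2 opens its list of laboratory analyses with "For each laboratory parameter, the following analyses will be performed" and exempts no parameter. Besides values, the list has three outputs that link a patient's baseline to later results:

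- a summary "on change from baseline to last post-baseline value under treatment";
- "Number and percentage of patients with at least one high/low emergent abnormal value under treatment", judged against reference ranges and PCSA cut-offs;
- a classification "using shift tables from baseline to the worst (high and/or low) values under treatment".

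Protocol 8.1 defines the laboratory examinations as "serum biochemistry and haematology, pregnancy tests, coagulation tests, cryoglobulins, urinalysis".

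The SAP splits these parameters. Section 4.4.2.1 covers haematology, biochemistry and coagulation in blood. It keeps all of the outputs above and adds listings of patients with emergent out-of-range values. Section 4.4.2.2 covers the rest, and its only analysis is: "For urinary biochemistry and cryoglobulins parameters, descriptive statistics on value at baseline, at each post-baseline visit under treatment and last post-baseline value under treatment".

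Under SAP 3.1, a qualitative result is summarised as the number and percentage of patients in each class, by treatment group. SAP 1.1.2 keeps "incidence of abnormal safety parameters throughout the study" within the secondary safety endpoint. SAP section 6 records several dropped analyses (inference on MFI, SF-36 and stimulated salivary flow, the biopsy description, the PBMC subsets), but not this one.

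**The concern.** Dipstick results are semi-quantitative classes, and a cryoglobulin result is absent or present, with a type if present. A class table by visit counts the patients abnormal on each occasion. It does not say whether they are the patients who were abnormal before treatment. A patient who turns positive can be offset by one who turns negative, and the table does not move.

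This is the first trial of S95011 in patients with primary Sjögren's syndrome. How many patients developed urinary protein or blood, or cryoglobulins, on each arm is an ordinary safety question. The protocol's analysis text would answer it in a pre-specified table; the SAP's text would not. Because the omission is undeclared, a reader of the eventual report cannot tell whether it was a decision or an oversight.

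**Working it through.** The documents give no figure to reproduce here. The first step is a comparison of texts. I read the SAP's urinary biochemistry as the protocol's urinalysis.

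| Output | Protocol 10.1.2.5.2, each laboratory parameter | SAP 4.4.2.1, blood | SAP 4.4.2.2, urine and cryoglobulins |
|---|---|---|---|
| Values at baseline, each visit and last on treatment | yes | yes | yes |
| Change to last value | yes | yes | no |
| Patients with an emergent abnormal value | yes | yes | no |
| Shift table, baseline to worst | yes | yes | no |

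The second step is to see what the remaining tables can tell about new cases. The inputs are n patients in an arm, b positive at baseline and v positive at a later visit, with no missing results.

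- One visit: the number newly positive lies between max(0, v − b) and min(v, n − b).
- Several visits: the number ever newly positive lies between max(0, largest v − b) and min(n − b, sum of v).

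The arm sizes, 30 and 15, are the planned ones (protocol 10.2). The counts are assumed, because the documents give none.

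| n | b | v | Newly positive at that visit |
|---|---|---|---|
| 30 | 3 | 3 | 0 to 3 |
| 30 | 6 | 6 | 0 to 6 |
| 30 | 3 | 6 | 3 to 6 |
| 30 | 0 | 3 | exactly 3 |
| 15 | 2 | 2 | 0 to 2 |

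Cryoglobulins are measured at W000, W004 and W013 (and at screening). Take 3 of 30 positive at each of these three visits.

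- Lower bound: max(0, 3 − 3) = 0. The same three patients are positive throughout.
- Upper bound: min(30 − 3, 3 + 3) = min(27, 6) = 6. Three patients are new at W004 and three others at W013.

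The last on-treatment value does not narrow this. For a patient with a W013 result, it is the W013 result.

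The tables are not empty of information. They bound the number of new cases and show the net change in prevalence. In special cases, such as no positives at baseline and a single later visit, they fix the number. Urinalysis has five scheduled visits after the first dose up to W013 (W002, W004, W007, W010, W013), so equal counts per visit leave it more loosely bounded than cryoglobulins.

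**The case against.** A reader might infer that new proteinuria, haematuria or cryoglobulinaemia cannot be counted in this trial, or that part of the secondary safety endpoint cannot be reported. The documents support neither. Results are collected per patient, so emergence can be derived at any time. The endpoint in SAP 1.1.2 speaks of abnormal parameters, not newly abnormal ones; emergence comes from the protocol's analysis text.

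There is also other cover:

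- Under protocol 8.2, clinically significant abnormalities after the first dose are recorded as adverse events, and so reach the TEAE tables.
- Serum creatinine and urea keep their emergent counts and shift tables.
- Cryoglobulinaemia scores in the ESSDAI biological domain and proteinuria in the renal domain. SAP 4.3.7 describes the domains by value and change.

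This cover is real but partial. A dipstick abnormality without symptoms, judged not significant and needing no therapy, is not an adverse event under protocol 8.2. In the biological domain, cryoglobulinaemia shares its level with IgG above 20 g/l, so a new case cannot be isolated. The renal domain grades proteinuria in g/day, excludes involvement unrelated to the disease, and is scored after baseline only at W004 and W013.

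The most substantial objection is that the protocol's outputs do not carry over unchanged. Its emergent counts rest on reference ranges and PCSA cut-offs, and the documents give none for dipstick classes or cryoglobulins. Numeric change means little for classes. Protocol 8.1 also lists pregnancy tests in the same place, and nobody would expect a shift to worst value for those. This stands as a reason to adapt the outputs. It does not explain dropping them without a note.

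Finally, renal toxicity and cryoglobulinaemia are not among the protocol's named risks or adverse events of special interest, and the table templates are in a separate document not seen here. Both points limit the weight of the finding. Neither changes what the SAP text specifies.

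**Conclusion.** The point holds as a gap in the pre-specified tables. For urinalysis and cryoglobulins, SAP 4.4.2.2 omits the emergent-abnormal counts and baseline-to-worst shift tables that protocol 10.1.2.5.2 plans, and section 6 does not say so. Followed as written, the laboratory tables give prevalence and its net change, but not the number of patients newly abnormal.

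The size can only be illustrated: 0 to 6 newly positive patients of 30 behind one and the same cryoglobulin table, on assumed counts of 3 per visit and complete data. The upper end needs complete turnover between visits and is a bound, not an expectation.

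The SAP already uses the right tool elsewhere. Section 4.5.1 cross-tabulates autoantibody status at baseline against W013 to show how many patients moved, and section 4.3.7 does the same for ESSPRI classes. Categorical safety results deserve the same treatment.

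**What to change.** In SAP 4.4.2.2, keep the existing tables and add, by arm and analysis period:

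- the number and percentage of patients negative or normal at baseline with at least one positive or abnormal on-treatment result;
- a shift table from baseline class to worst on-treatment class.

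Apply both to cryoglobulins (negative/positive) and to dipstick parameters with a clear normal/abnormal split, such as protein, blood, glucose and leukocytes. Leave out pH and specific gravity. State how a missing baseline is treated; SAP 3.2 lets it count towards emergence for parameters with reference ranges.

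List urine microscopy results rather than tabulating shifts. Protocol 8.1 calls for microscopy only after an abnormal dipstick, so a patient with a normal baseline dipstick would have no baseline microscopy.

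Record in SAP section 6 any protocol output not carried over for these parameters, such as numeric change and PCSA-based counts, with the reason.

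The cost is SAP wording and a categorical table template, with no new data. The small downside is mapping local dipstick grades to common categories, which should be settled before the results are tabulated by arm.

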4.4.3. Vital signs, clinical examination and other observations related to safety

4.4.3.1. Vital signs and clinical examination

Definition:

The following vital signs and clinical examination will be analysed:

- Weight (kg).
- BMI (kg/m²).
- Body temperature (°C).
- SBP (mmHg) before IMP infusion (and 2h after IMP infusion for W000 and W002).
- DBP (mmHg) before IMP infusion (and 2h after IMP infusion for W000 and W002).
- HR (b.p.m) before IMP infusion (and 2h after IMP infusion for W000 and W002).

Analysis:

Vital signs and clinical examination will be described, in terms of value at baseline, value at each post-baseline visit under treatment as well as in terms of change from baseline to each post baseline visit under treatment.

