4. STUDY DESIGN

This is a phase IIa, international, multicentre, randomised (2:1), double-blind, placebo-controlled study.

The study will consist of:

- **Screening period without study treatment:** within 28 days prior to W000, after signing the informed consent, in order to check eligibility of patients.
- **Randomised and double-blind treatment period:** from W000 to W013 (study drug administration at W000, W002, W004, W007, W010) with 2-parallel groups (750 mg of S95011 and matching placebo), with stratification by baseline intake of oral corticosteroids (yes/no) and baseline intake of antimalarial (e.g. chloroquine, hydroxychloroquine, quinacrine) (yes/no).
- **Safety follow up period without study treatment:** 15 weeks with one visit at W019 and one at W028. This follow-up period will allow sufficient time for monitoring safety until 5 half-lives of S95011. In addition, it is anticipated that more than 97% of patients have RO < 95% at W028 (meaning that almost no pharmacological effect of the product is expected).

The expected duration of patient participation will be 32 weeks maximum.

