8.2. Methods and measurement times

- **Physical examination:** will be performed at ASSE, W000, W002, W004, W007, W010, W013, W019, W028.
- **Vital signs (pulse, blood pressure, body temperature):** will be assessed after 5 min rest, in supine position Blood pressure will be measured preferably on the same arm. All devices routinely used in the centre to measure blood pressure are accepted.

Vital. signs will be performed at ASSE, W000, W002, W004, W007, W010, W013, W019, W028.

On the days of administration, the physical examination and vital signs will be performed:

- pre-dose
- and post dose (before discharge): at W000 and W002, patients will be monitored closely for 2 hours after completion of IV infusion (or longer, at the discretion of the Investigator) for vital signs, and signs or symptoms of adverse events including development of an injection reaction. At all other visits with IMP administration (W004, W007, W010), post dose assessments will similarly include assessing infusion site, physical examination and vital signs before dismissing the patient from the clinical site.

- **Body weight (kg):** will be measured with an empty bladder, the patient being in indoor clothing, without shoes at ASSE, W000, W004, W010, W013, W019, W028.
- **12-lead ECG:** A standard 12 lead ECG will be recorded in lying position after 5-10 minutes rest. The investigator or designated physician will review and sign all ECGs. Once signed, the original ECG tracing will be retained with the patient's source documents. At the request of the Sponsor, a copy of the original ECG will be made available.

Clinically significant ECG abnormalities, as judged by the investigator, will be recorded on the relevant medical history CRF page prior to first dosing and on the Adverse Events page thereafter.

12-Lead ECG will be performed at W000, W004, W010, W013, W019, W028.

On the days of administration, the 12-lead ECG will be performed pre-dose.

- Laboratory examinations

Laboratory tests analysis will be subcontracted to a central laboratory except for assessments such as infectious disease panel, HBA1c, tuberculosis test and for ESR, cryoglobulins, urinalysis and pregnancy tests. The details for sampling, handling, storage and shipping of the samples will be described in a laboratory manual.

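### Vital signs are taken after all five infusions, but the SAP summarises post-infusion values at only two, without temperature, a same-day change at W002 or any count of abnormal values

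*SAP*

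**What the plan says.** Collection. Protocol 4 sets five infusions: "study drug administration at W000, W002, W004, W007, W010". Protocol 8.2 defines the parameters as "Vital signs (pulse, blood pressure, body temperature") and requires them both pre-dose and post-dose on administration days. For the first two infusions, "at W000 and W002, patients will be monitored closely for 2 hours after completion of IV infusion". For the rest, "At all other visits with IMP administration (W004, W007, W010), post dose assessments will similarly include assessing infusion site, physical examination and vital signs", ahead of the patient leaving the site. Protocol 6.1 and the footnotes to the investigation schedule agree.

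Analysis. SAP 4.4.3.1 lists "SBP (mmHg) before IMP infusion (and 2h after IMP infusion for W000 and W002"). It lists DBP and heart rate in the same form, with post-infusion values at the same two visits only. Body temperature is listed with no infusion time point. The planned statistics are the baseline value, the value at each later visit under treatment, and the change from baseline. SAP 3.2 defines baseline as one value per patient, the last analysable one before the first dose.

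Endpoint. SAP 1.1.2 describes the safety endpoint as adverse events plus "change over time in safety parameters (vital signs, biological laboratory) and incidence of abnormal safety parameters throughout the study". Protocol 3.4 has the same structure, and Protocol 8.1 lists vital signs among the safety parameters. SAP 4.4.2.1 plans counts of patients with emergent abnormal values for haematology, biochemistry and coagulation. SAP 4.4.3.1 plans none for vital signs.

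**The concern.** Post-infusion readings are taken because of a named risk. The benefit-risk part of Protocol 2 names acute hypersensitivity, gives hypotension as one of its symptoms, and counts post-dose vital signs at the later infusions among the mitigations. It also says that cytokine release syndrome cannot be ruled out. For three of the five infusions the SAP plans no arm-level summary of those readings, and for temperature it plans none after any infusion.

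At W002 the comparator is the weaker of two available. A change from study baseline mixes what happened during the infusion with two weeks of drift. One component of the stated endpoint, incidence of abnormal values, also has no planned vital-sign table. What is at stake is the ability to compare the arms on modest shifts that no investigator would report as an event.

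**Working it through.** The plan states no figure on this point, so the check compares what is collected with what is summarised.

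**Inputs**
- Infusion visits with post-dose vital signs: 5 (Protocol 4 and 8.2).
- Parameters: SBP, DBP, pulse or heart rate, temperature = 4 (Protocol 8.1 and 8.2).
- Post-infusion summaries planned: SBP, DBP and HR at W000 and W002 (SAP 4.4.3.1).
- Planned patients: 30 on S95011, 45 in all (Protocol 10.2).

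**Coverage**

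| Quantity | Collected | Summarised | Share |
|---|---|---|---|
| Infusion visits | 5 | 2 | 2/5 = 40% |
| Parameter-by-visit cells | 4 × 5 = 20 | 3 × 2 = 6 | 6/20 = 30% |
| Reading sets, S95011 | 30 × 5 = 150 | 30 × 2 = 60 | 90 not covered |
| Reading sets, both arms | 45 × 5 = 225 | 45 × 2 = 90 | 135 not covered |

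The last two rows assume that every patient receives all five infusions, so they are upper limits. They count a set as covered when SBP, DBP and HR are summarised, even though temperature is not.

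**Comparator.** Let B be the study baseline, P the W002 pre-dose value and Q the W002 value 2 h after infusion. The planned change is

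Q − B = (Q − P) + (P − B).

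Only Q − P reflects that day's infusion; P − B is drift since baseline. At W000, B is normally that day's pre-dose reading, so the planned 2 h change is already a within-visit change. The comparator problem therefore affects W002 now, and would affect W004, W007 and W010 if they were added without a within-visit change.

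**Abnormal values.** Emergent-abnormality tables for vital signs in SAP 4.4.3.1: 0. The definitions in SAP 3.2 are introduced as applying to safety endpoints other than adverse events, but they are worded for laboratory ranges and the sponsor's cut-offs for potentially clinically significant values. The parameters whose limits are itemised in SAP 7.2.3.2 are laboratory ones, and no vital-sign cut-offs appear.

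**The case against.** Much of the case on the other side is sound.

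- **Reactions are captured elsewhere.** Clinically relevant abnormal findings are adverse events (Protocol 8.3). Allergic or infusion-related reactions of grade 3 or higher, and any cytokine release syndrome, are events of special interest (Protocol 8.6). SAP 4.4.1 tabulates both by arm and describes emergent events by time to onset. A reader might infer that the trial cannot show effects of the later infusions; the documents do not support that. What stands is that this route depends on investigator judgement or a grade threshold and does not compare the readings themselves.
- **The protocol has the same gap.** Protocol 10.1.2.5.3.1 plans only values and change from baseline. A reader might infer an undeclared departure in SAP section 6, but no protocol-planned vital-sign analysis was clearly removed, so there was nothing clear to declare.
- **Temperature is analysed by visit.** Only a post-infusion time point is missing.
- **The endpoint wording is loose.** Its bracketed list follows change over time, not incidence. But Protocol 8.1 makes vital signs safety parameters, so incidence of abnormal safety parameters reasonably includes them.
- **Timing differs.** The later post-dose readings have no fixed time, and the documents do not confirm that the values reach the database. This argues for a footnote and a condition, not for omission.
- **The W002 mean can be recovered.** The pre-infusion change from baseline is also planned, so mean(Q − B) minus mean(P − B) gives mean(Q − P) when the same patients contribute. Its spread and extremes cannot be recovered.
- **Immunogenicity adds little.** A reader might infer that anti-drug antibodies make the later infusions riskier. In the multiple-dose part of the phase I study they appeared on Day 57 (6 mg/kg) or Day 85 (10 mg/kg). W004 and W007 (about Days 29 and 50) precede both. The point does not rest on this.

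**Conclusion.** The point holds as a modest gap in the systematic safety summary. SAP 4.4.3.1 states a rule that leaves out post-infusion SBP, DBP and HR at three of five infusions, specifies no post-infusion temperature, and at W002 uses the study baseline where a same-day value exists. Incidence of abnormal values, which the endpoint covers, is planned for laboratory parameters only. Detection of clinically relevant reactions and the primary analysis are unaffected.

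This assumes that the separate table templates, which were not available, follow the SAP text. It also assumes that the two W000 readings are told apart by time or label, because SAP 7.1.1 classifies untimed readings by date alone.

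**What to change.** In SAP 4.4.3.1:

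1. Summarise SBP, DBP, HR and temperature before and after infusion, by arm, at W000, W002, W004, W007 and W010, wherever the post-dose values are in the database.
2. Add the within-visit change, post-infusion minus pre-infusion, for each parameter and visit.
3. Footnote that post-dose readings at W004, W007 and W010 are taken before discharge and not at 2 h.
4. Add the number and percentage of patients with emergent abnormal vital signs by arm, using cut-offs that the sponsor fixes before unblinding.

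The cost is SAP wording and a few descriptive tables, with no new patient procedures. The drawback is less standardised timing at the last three infusions, so those summaries need more cautious reading.
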